## 3.2.8 Adherence Interview

Patients ages 12 and older and parents of patients 3-18 years will be asked to complete an interview via phone or video chat with one of the study investigators ideally between cycles 8 and 12 or at the time of coming off study (whichever is later). The qualitative interview will be recorded and transcribed in order to conduct content analysis, which may inform future adherence interventions. We will attempt to conduct interviews with everyone, with a goal of interviewing 80% of adult participants, 80% of participants 12-17, and 80% of parent participants. The interview contains 6 questions about barriers and facilitators to adherence and preferences for adherence interventions, and is expected to take between 15-30 minutes. See **Appendix J** and **Appendix K**.

Procedure	Baseline	Routine Treatment Protocol Re-Staging Visits	Other Timepoint	After 18 Cycles of treatment or at time patient is off treatment trial
Demographic Form	X			
Life Events Checklist	Х			
NF1 QOL	X			
Questionnaires				
(PROMIS)				
Medication Diary 		Х		
Pill Count Form 		Х		
MEMS Record Form 			X 	
Barriers to Adherence			$X^4$	X
Questionnaire 				
Adherence Interview 			X 	

## **3.3 Study Calendar**

 Will be given to patients/caregivers at baseline to complete only when pill bottle openings do not correspond to medication taking (**Appendix I**).

 Will be sent electronically to any subject who has < 90% medication adherence documented by MEMSTM systems (**Appendix F**). This questionnaire may be sent to a single subject more than once (each time adherence < 90% is identified). All patients will be sent the questionnaire after 18 cycles of treatment or at the time patient comes off treatment trial (whichever comes first).

 To be performed with primary caregiver of patients 3-18 and patients ages 18+ any time between cycles 8 and 12.

<sup>1To be completed by the patient and/or caregiver. Can use the Generic Medication Diary Form (Appendix G) or treatment protocol specific diary form

<sup>2 To be completed by the study team at the time of routine protocol re-staging visit (**Appendix K**)

# 3.4 COMPENSATION

After 12 cycles or when taken off treatment (whichever is earlier), participants will receive a small amount of money (\$25) to thank them for their time. Funds will be distributed in accordance with the Clinical Center's Research Volunteer system, such that participants can have the money directly deposited to a bank account or have a check mailed to them. If patients are taken off-study early (i.e., due to disease progression), we will still provide them with \$25 as long as they have completed the Barriers to Adherence questionnaire and phone interview (since the payment is offered to thank them for their time doing the questionnaire). They will also be paid an addition \$15 for completing the telephone interview as described above.

Based on the HRPP SOP Appendix B, participants will be compensated for completion of questionnaires (1.5 units = \$15) + Behavioral Tasks (using electronic monitoring caps and returning it to clinic; 1 unit = \$10) = \$25. Participants will be paid separately for a telephone interview (1.5 units = \$15).

# 3.5 OFF STUDY CRITERIA

Participants will be removed from this study for any of the following:

- Completion of protocol requirements (18 cycles of therapy completed and final questionnaire completed)
- Patient comes off treatment on the concurrently enrolled clinical trial for treatment of plexiform neurofibroma(s)
- Participant requests to be withdrawn from study
- Patient develops significant cognitive or emotional difficulties that would prevent them from being able to understand and/or participate fully in the study or complete the measures.
- Lost to follow up
- Investigator discretion
- Death
- If the patient meets an off-study criterion, then the adult/caregiver of that patient should also be removed from the protocol.

# **4 DATA COLLECTION AND EVALUATION**

## 4.1 DATA COLLECTION

The PI will be responsible for overseeing entry of data into an in-house password protected electronic system (Labmatrix and/or Excel) and ensuring data accuracy, consistency and timeliness. The principal investigator, associate investigators/research nurses and/or a contracted data manager will assist with the data management efforts. All data obtained during the conduct of the protocol will be kept in secure network drives or in approved alternative sites that comply with NIH security standards. Primary and final analyzed data will have identifiers so that research data can be attributed to an individual human subject participant.

Adverse events occurring as a result of treatment for the underlying condition or medical treatment for pain will NOT be recorded on this study.

**End of study procedures:** Data will be stored according to HHS, FDA regulations, and NIH Intramural Records Retention Schedule as applicable.

Loss or destruction of data: Should we become aware that a major breach in our plan to protect subject confidentiality and trial data has occurred, this will be reported expeditiously per requirements in section 5.2.1.

# 4.2 DATA SHARING PLAN

I will share coded, linked or identified data with approved outside collaborators under appropriate agreements; and coded, linked data will be shared at the time of publication and or public presentation.

# 5 NIH REPORTING REQUIREMENTS / DATA AND SAFETY MONITORING PLAN

# 5.1 **DEFINITIONS**

• Please refer to definitions provided in Policy 801: Reporting Research Events found here.

# 5.2 OHSRP OFFICE OF COMPLIANCE AND TRAINING / IRB REPORTING

# 5.2.1 Expedited Reporting

Please refer to the reporting requirements in Policy 801: Reporting Research Events and Policy 802 Non-Compliance Human Subjects Research found here.

5.2.2 IRB Requirements for PI Reporting of Adverse Events at Continuing Review

Please refer to the reporting requirements in Policy 801: Reporting Research Events found here.

# 5.3 NCI CLINICAL DIRECTOR REPORTING

Problems expeditiously reported to the OHSRP in iRIS will also be reported to the NCI Clinical Director. A separate submission is not necessary as reports in iRIS will be available to the Clinical Director.

In addition to those reports, all deaths that occur within 30 days after receiving a research intervention should be reported via email to the Clinical Director unless they are due to progressive disease.

To report these deaths, please send an email describing the circumstances of the death to [name] at [contact] within one business day of learning of the death.

# 5.4 NIH REQUIRED DATA AND SAFETY MONITORING PLAN

# 5.4.1 Principal Investigator/Research Team

The clinical research team will meet on a regular basis to ensure that study implementation and follow up data collection are organized and completed in a timely fashion. The principal investigator and/or AI will review all data within one week of submission. Events meeting requirements for expedited reporting as described in section **5.2.1** will be submitted within the appropriate timelines.

The principal investigator and lead AI will review adverse event and response data on each patient to ensure safety and data accuracy. The principal investigator will personally conduct or supervise the investigation and provide appropriate delegation of responsibilities to other members of the research staff.

## **6** STATISTICAL CONSIDERATIONS

## 6.1 PRIMARY ENDPOINT

The primary endpoint is to determine the proportion of enrolled patients for which we can collect data from the MEMSTM system for two or more cycles of treatment. It would be desirable and the MEMS system considered feasible in this setting if this were to equal or exceeds 75%.

# 6.2 SECONDARY ENDPOINTS

- 6.2.1 Average percent adherence based on the MEMSTM data only for cycles 1-4, 5-8, 9-12 and 13-18
- 6.2.2 Relationships between adherence (correlations, t-tests, etc.) and demographics, life events and barriers to adherence will be used to identify patient characteristics that may predispose to poor medication adherence

# 6.3 EXPLORATORY ENDPOINTS

- 6.3.1 Average adherence rates calculated from the pill counts, patient diaries and MEMSTM caps will be compared
- 6.3.2 Response to therapy will be defined as either a partial or complete response as per the primary clinical trial on which they are being treated. Response rates will be compared between patients that are adherent to medication (≥90% adherence by MEMSTM) with patients that are non-adherent to medication (<90% adherence by MEMSTM)
- 6.3.3 Average adherence rate (based on MEMSTM data) for patients  $\leq 12$  and those > 12 years old. Propose to use twelve years old as a cut-off point since adherence often declines during adolescence

Qualitative analysis of data from adherence interviews to determine needs of patients on NF clinical trials to improve adherence

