### **1.2 BACKGROUND AND RATIONALE**

### 1.2.1 Emerging Therapies in Neurofibromatosis Type 1

Neurofibromatosis 1 (NF1) is an autosomal dominant disorder with an incidence of 1:3500 in the United States. One of the cardinal features of NF1 is the development of histologically benign peripheral nerve sheath tumors called plexiform neurofibromas (PN) in 25-50% of individuals with NF1. PN are a major source of morbidity for many patients. The only current standard treatment for these tumors is surgical resection, yet many of the tumors are inoperable as they are often infiltrative and intertwined with vital vascular and nervous system structures. Recent studies of selumetinib (AZD6244), an oral specific MEK1/2 inhibitor, have shown promise in the treatment of PN. As this drug and other potential therapeutic options become available for this unique patient population, assessing and ensuring adherence with prescribed medication regimens will be essential, with implications for clinical trials and for prescribed usage. The current study aims to (1) document longitudinal patterns of adherence to oral therapy for PNs among children, adolescents, and young adults with NF1, and to (2) identify patient characteristics and/or time periods during therapy that are associated with an increased risk of medication non-adherence.

The occurrence of PN tumors in NF1 cause substantial morbidity, including, but not limited to, disfigurement, impairment of nerve function, and pain3.4. MEK inhibitors, such as selumetinib, inhibit the activity of isolated MEK to phosphorylate extracellular signal-regulated kinase (ERK) 2 in enzyme assays. In the Phase I portion of the NIH study of selumetinib for pediatric patients with inoperable plexiform neurofibromas, 17 of 24 patients (71%) had confirmed partial

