#### 1.2.3 General Overview

This study will recruit children and adults with NF1 who are enrolled in a current or future treatment protocol for a drug targeting PN reduction. Patients will be invited to participate during a routine treatment protocol-mandated visit, ideally within one cycle of starting study drug. During this visit, patients (and caregivers of child patients) will complete a series of questionnaires as described in section **3.2**. The patients will also be instructed to begin using the medication event monitoring system (MEMSTM) for the clinical trial drug only at initiation of study drug (or at beginning of next cycle) that will provide the researchers with a more objective measure of adherence for the study drug.

MEMSTM data will be collected at all routinely scheduled protocol re-staging visits (e.g., baseline, pre-cycle 5, pre-cycle 9, pre-cycle 13, and pre-cycle 19) which will include measurements of tumor volume. During these appointments, patients will return their MEMS caps and data from the caps will be uploaded onto a computer software system. These data will capture percentage of doses taken (doses taken/doses prescribed X 100).

Following each study visit, rates of adherence from the diaries, pill counts, and MEMSTM caps will be compared. If one or more methods suggest an adherence rate of less than 80%, the PI of the medical trial will be notified.

If the MEMSTM caps indicate medication adherence of <90% for one or more cycles of therapy, or another method (e.g., diaries) indicates <80% adherence, the patients will be electronically sent a Barriers to Adherence Questionnaire (**Appendix F**) to help pinpoint potential medication adherence related issues. This will be sent to the subject ideally within one week but no later than one month of the study data being received by the NIH team.

All patients will be invited to participate in individual interviews focused on medication adherence issues, either between cycles 8-12 or at the time of coming off study (whichever is later). For all patients, the interviews will focus on the issues leading to any missed doses (if applicable) as well as to gauge what the best approach might be to address these issues in a future interventional trial. We also will ask patients if they encountered any barriers to medication adherence during the course of the trial and if so, what techniques they used to overcome them.

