Patients/caregivers will be given a form to complete any time they take a dose of medication that does not correspond to a pill bottle opening (Appendix I) Patients will also be asked to complete a self-report daily diary of medication adherence throughout treatment or through 18 cycles of therapy (whichever is shorter) and pill counts will be performed at all standard treatment protocol visits during this time. If diaries are included on the primary treatment protocol, these will be utilized. If not, a generic diary (Appendix G) form will be provided. The pill count form (Appendix H) should be completed by the study team for each cycle for all participants, as this also contains information regarding any dose adjustments or changes. These forms should be collected/completed by the study team during each routine treatment protocol mandated follow up appointment. In addition, at these visits patients will return their MEMSTM caps and data from the caps will be uploaded onto a computer software system before being returned to the patient during that same visit. Although not anticipated, if there are scheduling difficulties prohibiting the return of the cap before the patient leaves the center, we will send the cap to the patient/family via Federal Express. It is recommended, but not required, that a patient bring their MEMS cap to any of these visits, if a patient forgets we will collect the data at the next visit during which they bring the cap to clinic.

Results of evaluations for disease response as per the primary treatment protocol will be recorded (e.g. tumor volume) at all restaging evaluations through 18 cycles of therapy. The response criteria defined by each specific treatment protocol will be used to determine if the patient had stable disease, partial response, complete response or disease progression while on study therapy.

[figure not shown]
Following each study visit, rates of adherence from the diaries, pill counts, and MEMS caps will be compared. If one or more methods suggest an adherence rate of less than 80%, the PI of the medical trial will be notified via secure email or phone.

Patients with MEMS cap data indicating <90% adherence will be sent a Barriers to Adherence Questionnaire (Appendix F) electronically as close in time as possible (ideally within one week

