# 6.6 ANALYSIS OF EXPLORATORY ENDPOINTS

Patients who are enrolled onto this trial will have the fraction of the total times that their medication is intended to be taken determined and reported with descriptive statistics based on results obtained using the MEMSTM system. This will be determined per patient as a percentage of the total planned medication administrations during all doses for which the patient is enrolled on the trial and eligible to be receiving medication. All study team directed medication holds and/or dose changes will be documented on the Pill Count Form (**Appendix H**) and will be used to determine the total planned medication administrations.

For each patient, there will be a percentage of total planned medication administrations calculated separately for cycles 1-4, cycles, 5-8, cycles 9-12 and cycles 13-18. Despite the limited number of patients to be enrolled, paired difference in the percentages between cycles 1-4 vs. 5-8, cycles 9-12 vs. 13-18, and cycles 1-4 vs. 9-12 will be formed for all patients during all evaluable cycles and reported using descriptive statistics. The calculated differences in adherence rates between time points will also be tested for being equal to zero using a Wilcoxon signed rank test, and interpreted as exploratory because of the limited amount of data.

The adherence rates as determined by the pill counts and the patient diaries will be recorded, and the agreement between these two measures and the MEMSTM percentages will be evaluated using exploratory and descriptive statistical methods. For example, the difference between two measures reporting the fraction of intended doses for a given set of three cycles will be reported and may be displayed graphically or formally tested using a paired analysis.

The analyses for all other secondary and exploratory objectives will be descriptive. Graphical presentations, such as histograms, stem and leaf plots, and scatterplots may be generated as appropriate to the type of endpoint.

- Transcriptions of individual interview will be created and analyzed descriptively using NVivo software.
- We will calculate and describe the percent medication adherence as documented by pill count, patient diary and using the MEMSTM system

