# 6.8 SUBJECT ACCRUAL

We anticipate accrual of approximately 12-15 patients.

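### Exploratory endpoint 6.3.2 compares only PR/CR yes or no between adherence groups; adding the tumour-volume change recorded at restaging would use more of the data (low severity, optional)

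*Combined protocol and SAP*

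**What the plan says.** Section 6.3.2 sets the outcome, "Response to therapy will be defined as either a partial or complete response as per the primary clinical trial", and the contrast: "Response rates will be compared between patients that are adherent to medication" (at least 90% by MEMS) and those below 90%.

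Volume data are collected. Section 1.2.3 says of the restaging visits, "which will include measurements of tumor volume". Section 3.1 adds "Results of evaluations for disease response as per the primary treatment protocol will be recorded (e.g. tumor volume) at all restaging evaluations", through 18 cycles. It also says how the categories are assigned: "The response criteria defined by each specific treatment protocol will be used to determine if the patient had stable disease, partial response, complete response", or progression.

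On analysis, Section 6.6 says "The analyses for all other secondary and exploratory objectives will be descriptive" and allows scatterplots where they suit the endpoint. It names no volume outcome. On size, Section 6.8 says "We anticipate accrual of approximately 12-15 patients". No test, significance level, power or effect size is given for this comparison.

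**The concern.** Section 1.2.2.1 gives the possible link between tumour response and adherence as one reason for using MEMS. The worry in Section 1.2.2 is regrowth after missed or held drug, which is a matter of degree. A PR/CR indicator cannot show degree. A patient whose tumour shrinks but falls just short of a partial response counts the same as one who progresses, although Section 3.1 records stable disease and progression separately. With 12–15 patients split at 90% adherence, little can be learned from a yes/no outcome, while a finer measure of the same thing is already being recorded. At stake is how much this exploratory comparison can suggest for later work. The primary feasibility decision is not affected.

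**Working it through.** **The plan's own figure.** There is none for this comparison. The only operating figure in Section 6 belongs to the primary endpoint: 9 or more successes of 12 at a true rate of 50%. It reproduces: (220 + 66 + 12 + 1)/4096 = 299/4096 = 7.3%. It has no bearing on 6.3.2.

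**Inputs.**
- Outcome: PR/CR yes or no (6.3.2).
- Sample: 12–15 (6.8).
- Response rate p: the only one in the documents is "17 of 24 patients (71%) had confirmed partial" responses in phase I (Section 1.2.1), so p = 17/24 = 0.708. Using it here is an assumption; 50% is taken as the other end of the range.
- Distribution of volume change: not given; normal is assumed first, then varied.

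**Step 1: expected non-responders at p = 17/24.** 15 × 7/24 = 4.4 and 12 × 7/24 = 3.5, so about four.

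**Step 2: efficiency under normality.** For a shift between two groups, the large-sample efficiency of the yes/no outcome relative to comparing means is φ(z)²/[p(1−p)], where z is the normal quantile at p.
- p = 0.50: 0.3989²/0.25 = 0.637, a loss of 36%.
- p = 17/24: z = 0.549, φ(z) = 0.3432, and 0.1178/0.2066 = 0.570, a loss of 43%.
- Equivalent sample: 12 × 0.570 = 6.8 up to 15 × 0.637 = 9.5, roughly 7–10.
- More extreme rates lose more: 51% at a response rate of 20% or 80%, and 66% at 10% or 90%.

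**Step 3: other distributions at p = 17/24.** The general formula is f(c)²·Var/[p(1−p)], where c is the response cut.

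| Distribution | Efficiency | Loss |
|---|---|---|
| Uniform | 0.403 | 60% |
| Normal | 0.570 | 43% |
| Logistic | 0.680 | 32% |
| t, 5 df | 0.780 | 22% |
| Laplace | 0.824 | 18% |

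The benchmark is a comparison of means. With a sharply peaked (Laplace) distribution cut exactly at its centre (p = 0.50), the ratio is 2.0, so the yes/no outcome would do better than means. A loss is therefore usual but not guaranteed.

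**Step 4: against a rank-based comparison, as proposed in the fix.** Under normality its efficiency relative to means is 12·Var·(∫f²)² = 3/π = 0.955. The yes/no outcome then has 0.637/0.955 = 0.667 at 50% and 0.570/0.955 = 0.597 at 71%, a loss of 33–40%.

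**Step 5: illustrative power.** The group sizes, the effects and both tests are assumptions, because the plan states none. Two-sided 5%, normal volume change, overall response rate 71%:

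| Adherent v non-adherent | True difference | Exact rank-sum on volume | Fisher on PR/CR |
|---|---|---|---|
| 10 v 5 | 1.5 SD | 64% | 38% |
| 8 v 4 | 1.5 SD | 57% | 25% |
| 10 v 5 | 1.0 SD | 32% | 17% |
| 8 v 4 | 1.0 SD | 29% | 10% |

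In runs with no effect (n = 15, 3–5 non-adherent), Fisher's actual size was about 1–2%, against about 3–5% for the rank-sum test. Part of the gap in the table is therefore Fisher's conservatism and not lost outcome information.

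**The case against.** The strongest reply is that this is an unpowered, descriptive, exploratory endpoint in a feasibility study of 12–15 patients, and no outcome scale removes that limit. This stands: at a 1.0 SD difference, volume raises the illustrative power only to about 30%.

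A second reply is that response by each parent trial's criteria is a defensible common currency when patients come from different treatment protocols, whereas pooled percent change mixes drugs and populations. This also stands. It is a reason to keep PR/CR and to mark the parent trial in any plot, but not to leave volume out. Parent-protocol criteria may themselves differ, so the yes/no outcome is not free of the same problem.

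Third, Section 6.6 already permits scatterplots. It does so in general terms, and nothing names volume change or which restaging visit would supply it.

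Some stronger readings are tempting and are not supported:
- A flat loss of about 40%. The documents contain no such figure; it depends on normality and a mid-range response rate.
- A nearly constant outcome. At 17/24 the binary variance is 0.2066, which is 0.2066/0.25 = 83% of its maximum. There are few non-responders, but the outcome does vary.
- The power gap as the cost of PR/CR alone. Section 6.6 makes this analysis descriptive, the plan names no Fisher test, and the two tests differ in actual size.

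**Conclusion.** The point holds as an efficiency weakness of low severity. Section 6.3.2 uses only PR/CR yes or no, tumour volume is recorded at restaging, and no section brings volume change into the adherence comparison. The loss is about 36–43% of the outcome information if volume change is roughly normal and the response rate is 50–71%, leaving 12–15 patients with the information of roughly 7–10. At 71% it ranges from 18% to 60% over the other distributions tried. The 71% comes from a single phase I study of one drug and may not apply to patients aged 3 to 59 on other oral agents.

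A reader might infer that the plan contains an error here, or that switching to volume would make the comparison adequate. Neither follows. No stated figure is wrong, the passages do not contradict each other, and precision stays low whichever outcome is used. The gain is a more informative description of the same few patients, specified before the data are seen.

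**What to change.** In Sections 6.3.2 and 6.6, add percent change in plexiform neurofibroma volume from the treatment-trial baseline as a further exploratory outcome.

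- **One prespecified summary.** Section 1.2.3 lists several restaging visits, and Section 3.5 takes patients off study when treatment stops, so the visit must be named. One choice is the change at the last restaging on treatment, up to completion of 18 cycles, so that patients who leave early contribute. State each patient's cycle at that visit, since time on treatment will differ.
- **Estimate.** Report the Hodges-Lehmann median difference between the two adherence groups with a 95% CI.
- **Plot.** Show every patient's volume change against continuous MEMS adherence, marked by parent trial. This also avoids relying only on the 90% cut.
- **Keep PR/CR.** Report response rates by parent-protocol criteria alongside.

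The cost is a wording change and slightly more analysis, with no new visit or measurement. Because Section 3.1 mentions tumour volume only as an example of what is recorded, the text should state that the volumes, including the treatment-trial baseline, are captured for every patient. The downside is that volume change is pooled across different drugs and parent trials, which the report should say.
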